## 1. **Protocol Summary**

Overall Design:	Open, randomized controlled trial

# 1.1. Synopsis

**Protocol Title:** Open randomized controlled phase 2 clinical trial for evaluation of safety and efficacy of COVID-19 convalescent plasma compared to standard care for treatment of COVID-19 disease in elderly patients in care homes.

Brief Title: Norwegian COVID-19 convalescent plasma treatment study in elderly patients in care homes.

Rationale: There is currently no approved and accessible treatment for COVID-19. Convalescent plasma from donors may provide a safe and effective treatment to reduce mortality, severity and duration of institutional care for elderly COVID-19 patients in care homes.

## **Objectives and endpoints**

Objectives	Endpoints
Primary	
Assess the effect of convalescent plasma on mortality in COVID-19	Primary endpoint: All-cause mortality within the first 28 days of observation. Secondary endpoints: All-cause mortality within 60 days of observation.
Secondary	
Effect of convalescent plasma on recovery time in patients with active COVID-19 infection	Time from intervention to negative SARS-CoV-2 PCR during a 28 days observation period.
Effect of convalescent plasma on clinical progression of COVID-19 disease	Requirement of oxygen therapy at days 1, 3, 7, 14, 21 and 28 compared to baseline. Change in NEWS score at days 1, 3, 7, 14, 21 and 28 compared to baseline.
Exploratory	
Effect of convalescent plasma on biomarkers in COVID-19	Change in CRP and lymphocyte count at day 1, 3, 7 and 14 after intervention. Time to normalized CRP and lymphocyte count.
Safety of convalescent plasma in COVID-19	Incidence of adverse events.

Brief Summary:	The objective of this study is to evaluate the safety and efficacy of convalescent plasma treatment in symptomatic elderly COVID-19 patients in Norwegian care homes. Approximately 500 eligible participants will randomly
	allocated to either the intervention (Convalescent plasma and standard care) or control (standard care only) group in a 1:1 ratio. Participants will be followed up over a 60-day observation period.
Intervention Group and Duration:	Participants randomized to treatment group will receive convalescent plasma treatment within 2 days after randomization. They will be followed up for 60 days.
Data Monitoring Committee:	Yes
Project leader	[name], Oslo University Hospital
National coordinating institution:	Oslo University Hospital
Study sites:	Study sites are defined as the care home department of participating municipalities
Study monitor:	Clinical trial unit (CTU), Oslo University Hospital
Study setting:	Norwegian care homes for elderly patients in participating municipalities
Inclusion and exclusion criteria	
 
Inclusion criteria
 
1. Age >50 years
 
2. SARS-CoV-2 PCR positive in respiratory tract sample within 3 days before inclusion
 
3. Onset of symptoms within 7 days before intervention as assessed by the attending clinician,
 
4. Voluntary, informed and documented consent by patient or guardian
 

	
 
Exclusion criteria
 
1. Included in any other interventional study for the treatment of COVID-19
 
2. Allergic reactions to plasma products
 
3. Acute severe co-morbidity
 

	
 
4. Estimated life-expectancy <90 days prior to symptomatic COVID-19 as assessed by attending clinician.
 
5. Other reasons where the attending clinician deems trial participation to be against the best interest of the patient
 
	
Intervention	SARS-CoV-2 convalescent plasma (1 unit; ~200-300 mL) from blood donors who were diagnosed and have recovered from COVID-19 infection, tested and released according to criteria from the Norwegian Health Directorate.	
Description of groups	Group 1: Standard of care + convalescent plasma given according to criteria	
Criteria for interruption	Group 2: Standard of care There will be one interim analysis for efficacy after half of the patients (n=253) have completed the first 28 days of follow-up. The study will be stopped if the interim analysis demonstrates superiority of the intervention.	
	The steering committee can decide to interrupt the study early if the data monitoring committee recommends discontinuation for safety reasons	
Study duration	1. July 2020 – 30. June 2021	
Recruitment	To support the recruitment for the study, all COVID-19 RT-PCR confirmed patients who are or will be admitted to nursing homes are reported to the principal investigator. This will initiate the process to engage with the patient and / or relatives to offer participation.	
Supportive treatment allowed	Guidelines for the treatment of COVID-19 in nursing homes for this patient group are described by the Norwegian Institute of Public Health and local health authorities. The medical professionals responsible at the nursing home are responsible for providing the health care considered to be professionally required regardless of the purpose of the study.	
Participants' timeframe	The events in which study participants are planned to be engaged are described in section "Schedule of activities". Briefly, consent and enrolment will take place within 2 days of notification of the study team for patients fulfilling the case definition for a confirmed COVID-19 patient.	
	Randomization and plasma transfusion will take place immediately after enrolment, by an ambulant transfusion team. Blood samples will be taken at day 0, 1, 3, 7 and 14 in the study period. Oropharynx samples will be taken at day 0, 1, 3, 7, 14, 21 and 28 in the study period.	

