# 1.2. Schedule of Activities (SoA)

[figure not shown]
Procedure	Screening (up to intervention	Inter vention (day 0)		0	bserva	tion Peri	od (day	1-60)	
	day)	0	1	3	7	14	21	28	60
Informed consent	Х								
Inclusion and exclusion criteria	Х								
Randomization	Х								
Demography	Х								
Height and weight	Х								
Medical status and co- morbidities	Х								
Current medication	Х								
Blood samples*		X	Х	Х	Х	Х			
Oropharynx samples**		X	Х	Х	Х	Х	Х	Х	
Clinical assessment***		X	Х	Х	Х	Х	Х	Х	
Mortality registration								X	Х
Study intervention (plasma transfusion)		X							
AE and SAE review									Х

Activities are scheduled as presented in table and flow-chart below.

\* Blood: Hemoglobin, thrombocytes, leukocytes with differential count, CRP, anti-Spike IgG.

\*\*Oropharynx: RTPCR SARS-CoV-2.

\*\*\* Registration of oxygen therapy at all care homes, NEWS score where implemented in the care home routines.

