# **3. Objectives and Endpoints**

Objectives	Endpoints
Primary	
Assess the effect of convalescent plasma on mortality in COVID-19	Primary endpoint: All-cause mortality within the first 28 days of observation. Secondary endpoints: All-cause mortality within 60 days of observation.
Secondary	
Effect of convalescent plasma on recovery time in patients with active COVID-19 infection	Time from intervention to negative SARS-CoV-2 PCR during a 28 day observation period
Effect of convalescent plasma on clinical progression of COVID-19 disease	Requirement of oxygen therapy at days 1, 3, 7, 14, 21 and 28 compared to baseline Change in NEWS score at days 1, 3, 7, 14, 21 and 28 compared to baseline
Exploratory	
Effect of convalescent plasma on biomarkers in COVID-19	Change in CRP and lymphocyte count at day 1, 3, 7 and 14 in the study period. Time to normalized CRP and lymphocyte count
Safety of convalescent plasma in COVID-19	Incidence of adverse events

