## 6.2. Measures to Minimize Bias: Randomization and Blinding

**Sequence:** A randomization sequence will be generated in a computer program and associated with predefined rows of unique patient identification numbers and inserted into the electronic data capture system (EDCS). After the participant has consented the ambulatory team will be informed and will randomize the participant using the EDCS.

Implementation; The randomization list will be produced by the CTU at OUH.

**Blinding:** This is an open-label, randomized controlled trial with a plasma arm administered as a transfusion, and all participants and staff will thus know the intervention to which the patient is allocated.

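### The only values that can serve as baseline for oxygen use, NEWS, CRP and lymphocytes are scheduled after open-label randomisation, and nothing readable requires them to precede transfusion

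*Protocol*

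**What the plan says.** **Order of events.** Section 1.1 (Synopsis, participants' timeframe) states: "Randomization and plasma transfusion will take place immediately after enrolment, by an ambulant transfusion team. Blood samples will be taken at day 0". Section 6.2 has the ambulatory team informed once consent is given, after which it randomises through the data capture system. Section 7.1 places the single transfusion directly after consent. None of these passages names a baseline step before allocation.

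**Schedule (Section 1.2).** Randomisation is ticked in the column headed "Screening (up to intervention" day. Blood samples, oropharynx samples and clinical assessment have no tick there. Their first tick is day 0, the column that also holds the row "Study intervention (plasma transfusion". The footnotes give the content of each item (CRP, differential count and anti-Spike IgG in blood; oxygen therapy and, where implemented, NEWS in the clinical assessment). They give no order within day 0. The synopsis repeats the timing for blood: "Blood samples will be taken at day 0, 1, 3, 7 and 14 in the study period".

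**Interval to plasma.** Elsewhere the synopsis says: "Participants randomized to treatment group will receive convalescent plasma treatment within 2 days after randomization". That does not sit easily with the immediate sequence described in the participants' timeframe.

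**Blinding.** Section 6.2: "all participants and staff will thus know the intervention to which the patient is allocated".

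**Endpoints (Section 3).** The first clinical-progression endpoint reads: "Requirement of oxygen therapy at days 1, 3, 7, 14, 21 and 28 compared to baseline". NEWS is worded in the same way. The exploratory endpoint is change in CRP and lymphocyte count, with no reference value named. Baseline is not defined anywhere in the protocol.

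**The concern.** A change from baseline compares arms fairly only if the baseline could not have been affected by the arm. Here the only measurement earlier than day 1 is scheduled after an open allocation.

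The risk differs by endpoint:

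- **Oxygen and NEWS (secondary).** Whether a resident is on oxygen is a staff decision, and the scoring is done by staff who know the arm. Either can shift the recorded baseline, and the shift passes into the change.
- **CRP and lymphocyte change (exploratory).** Knowing the arm does not plausibly alter an assay. Sampling after plasma could, and so could sampling up to 2 days after randomisation in one arm against an undefined day 0 in the other.
- **Anti-Spike IgG.** This is sampled on day 0 but is not a listed endpoint. If drawn after plasma it could contain donor antibody, and the patient's own pre-treatment serostatus would then be lost, in the plasma arm only.

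The order of collection is fixed by the protocol. A statistical analysis plan can define baseline, but it cannot supply a measurement that was not taken before allocation.

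**Working it through.** The plan states no figure on this point, so there is none to reproduce. The check is mainly one of reading.

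**1. Is there a pre-randomisation value?** The screening column holds consent, eligibility, randomisation, demography, height and weight, medical status and current medication. It holds no oxygen status, NEWS or study blood sample. Day 0 is the only candidate for baseline.

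**2. Does any text place day 0 measurements before randomisation?** No. Sections 1.1, 6.2 and 7.1 run from consent to randomisation to transfusion.

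**3. Does any text place them before transfusion?** Only in part. Section 6.1 requires blood pressure, pulse, respiratory frequency and temperature before transfusion. That covers some of what feeds NEWS, but not oxygen use, a full NEWS or blood. It comes after randomisation and has no counterpart in controls.

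**4. Is day 0 the same in both arms?** It is the intervention day, and controls have no intervention. The synopsis counts the CRP and lymphocyte days from intervention, whereas Section 3 counts them in the study period.

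**5. How large could the effect be?** The protocol gives no SD and no expected shift, so the following is illustration only. Suppose a share *f* of the plasma arm has a recorded baseline shifted by *c* SD. The difference in mean change is then biased by *f* × *c* SD. Assume no true effect, *n* = 506/2 = 253 per arm, and a baseline-to-follow-up correlation ρ = 0.5, so that the change score has the same SD as the outcome.

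δ = *f* · *c* · √(*n*/2) / √(2(1 − ρ)) = *f* · *c* · √126.5 = 11.25 · *f* · *c*

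Two-sided type I error = 1 − Φ(1.96 − δ) + Φ(−1.96 − δ)

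| *f* | *c* | bias (SD) | δ | type I error |
|---|---|---|---|---|
| 0.10 | 0.1 | 0.01 | 0.11 | 5.1% |
| 0.25 | 0.2 | 0.05 | 0.56 | 8.7% |
| 0.50 | 0.2 | 0.10 | 1.12 | 20.3% |
| 1.00 | 0.2 | 0.20 | 2.25 | 61.4% |

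This applies to a continuous score such as NEWS. NEWS is recorded only where care homes use it, so the true *n* would be smaller and the inflation less.

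**6. Lymphocytes after plasma.** The protocol's volumes span 200 to 350 mL across sections. With an assumed blood volume *B* of 3.5 to 5.0 L and simple dilution, the count falls by *V*/(*B* + *V*). The range is from 200/5,200 = 3.8% to 350/3,850 = 9.1%. This arises only if the sample follows the transfusion.

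**The case against.** The strongest reply is that the protocol is silent on order within day 0 and does not say that samples follow plasma. One team visits, and the screening column runs up to the intervention day, so everything may happen in one visit with blood drawn first. Section 1.2 also refers to a flow-chart that is not shown in the available text and might give the order. This stands as far as it goes. It limits the claim about plasma to what could happen. It does not remove the point about allocation, because the readable text consistently goes from consent to randomisation with no assessment in between.

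Other parts of the reply also stand. Oxygen decisions on days 1 to 28 are just as open as those on day 0, so moving the baseline removes one source of bias and not the larger one. The shifts in the table are assumptions. An analysis of follow-up values alone would avoid the problem, but it would no longer be the endpoint in Section 3.

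Stronger readings are tempting but not supported:

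- **That every biomarker and progression endpoint is compromised.** Time to normalised CRP and lymphocyte count is not a change score, and anti-Spike IgG is not an endpoint.
- **That patients who die before day 0 are lost because of this schedule.** They have no follow-up value, so they have no change score under any ordering.
- **That a 2-day delay is the rule.** The synopsis gives both an immediate sequence and a 2-day allowance, and the two must be reconciled.

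**Conclusion.** The point holds as a timing weakness in the protocol and should be corrected. As scheduled, the baseline for two secondary endpoints (oxygen, NEWS) is recorded after open allocation. The reference for one exploratory endpoint (CRP and lymphocyte change) is not protected from sampling after plasma or at different times in the two arms. Treating day 0 as baseline is an inference, but no other time point carries these measurements.

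The bias is possible, not demonstrated. Its size cannot be derived from the documents. Under the stated assumptions it ranges from negligible (5.1% type I error) to serious (61.4%), depending on how many baselines shift and by how much. A reader might infer that the trial's main result is at risk. It is not: 28-day and 60-day mortality come from the death registry and use no baseline value.

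**What to change.** In Section 1.2 and the synopsis timeframe, order the steps as consent; then baseline oxygen status, NEWS (where used), blood and oropharynx samples; then randomisation; then transfusion in the plasma arm. Move the first tick for these rows ahead of randomisation.

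Require baseline oxygen status and confirmation of sampling to be entered in the eCRF, which already performs the randomisation, before the allocation is released.

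In Section 3, define baseline as this pre-randomisation value and define day 0 identically in both arms. Without a common day 0, an interval of up to 2 days to plasma would let a day 1 change counted from intervention span up to 2 + 1 = 3 days in one arm. Reconcile the two synopsis statements on the interval between randomisation and transfusion.

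The cost is schedule wording and one eCRF check. The same assessments and samples are taken, only earlier. The downsides are samples from the few who consent but are not randomised, and baseline work that must be staffed before the allocation step, since Section 6.2 now brings in the ambulatory team after consent in order to randomise.

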# 1.2. Schedule of Activities (SoA)

[figure not shown]
Procedure	Screening (up to intervention	Inter vention (day 0)		0	bserva	tion Peri	od (day	1-60)	
	day)	0	1	3	7	14	21	28	60
Informed consent	Х								
Inclusion and exclusion criteria	Х								
Randomization	Х								
Demography	Х								
Height and weight	Х								
Medical status and co- morbidities	Х								
Current medication	Х								
Blood samples*		X	Х	Х	Х	Х			
Oropharynx samples**		X	Х	Х	Х	Х	Х	Х	
Clinical assessment***		X	Х	Х	Х	Х	Х	Х	
Mortality registration								X	Х
Study intervention (plasma transfusion)		X							
AE and SAE review									Х

Activities are scheduled as presented in table and flow-chart below.

\* Blood: Hemoglobin, thrombocytes, leukocytes with differential count, CRP, anti-Spike IgG.

\*\*Oropharynx: RTPCR SARS-CoV-2.

\*\*\* Registration of oxygen therapy at all care homes, NEWS score where implemented in the care home routines.

## 2. Introduction

Since the first confirmed case in Norway on Feb 26th 2020 the number of cases rapidly increased over a one months' period. Currently, (May 26th) there are 8364 cases of confirmed infected, 235 deaths. Although currently under control scenarios prepared by the Norwegian Institute of Public Health indicates a risk of a second wave of cases in the coming months, exceeding the capacity to treat patients. The ability to provide satisfactory treatment to at-risk groups will then be severely impaired, and high mortality can be expected. Health workers may also be exposed to a high risk of infection. Infection prevention measures in the population have been effective, but on return to normalcy of school closures, kindergartens and businesses the number of cases is expected to increase further. The duration of a second wave of the epidemic is unknown and may last for 6-8 months, perhaps longer, depending on the effectiveness and overall societal acceptability of continuing physical distance measures. The physical distancing interventions have severe effects on health and finance, but it will likely be in effect in some degree until effective treatment or vaccines are available. However, availability of vaccines and new anti-viral drugs will be very restricted due to the universal desire to source these, and it is uncertain whether Norway when will be able to source these at a scale aligned with the estimated demand.

## 2.1. Study Rationale

Convalescent plasma in the treatment of infections was used during the H1N1 influenza pandemic of 1918-20 (McGuire&Redden 1918, Luke et al 2006). In the pre-antibiotics area convalescent plasma was also used to treat bacterial disease (Casadevall&Scharff 1995). Data from clinical trials using convalescent plasma during the SARS-CoV-1 epidemic demonstrated clinical improvements in the patients if transfused early. Two studies from 2020 that included 10 (Duan et al PNAS 2020) and 5 (Shen et al JAMA 2020) cases who were given SARS-CoV-2 convalescent plasma documented clinical improvements along several parameters. A matched control study in US patients showed benefit in non-intubated patients (Sean et al, 2020). The first randomized clinical study in China was terminated due to lack of effect in late stages (Li et al, 2020), but also reported potential benefits (Casadevall, Joyner & Pirofski, 2020). There are also reports of more anecdotal character. In the absence of any documented efficient drugs or vaccines it is highly rational to perform a clinical trial of the safety and efficacy of SARS-CoV-2 convalescent plasma. COVID-19 associated mortality is highest in patients older than 65 years. A randomized clinical trial in this risk group using convalescent plasma early after CoV-2 diagnosis will yield the highest probability of demonstrating an effect.

## 2.2. Background

Originating in Wuhan Province of China in late 2019, a new coronavirus named SARS-CoV-2 has spread throughout much of the world. The virus, which causes respiratory infection and in some a serious respiratory illness, was declared a pandemic by WHO in March. As of ultimo May 2020, the number of detected infected is approaching 5,5 million worldwide, and more than 350,000 people have died. In addition, the numbers of actual infected are underestimated as adequate testing in large parts of the world is impossible and a substantial number of cases are

asymptomatic. In Norway, drastic measures have achieved a controlled spread of virus, and we are currently able to treat the number of patients within the total hospital care capacity, including intensive care units. However, it must be assumed that the spread of infection will continue and that a significant number of patients will die before vaccines become available. Although most people experience mild infection, serious illness and high mortality has been observed especially among the elderly, individuals with comorbidities such as cardiovascular disease, diabetes and obesity.

As per end of May 2020, about 90% of the 235 deaths reported in Norway due to COVID-19 had occurred between patients aged 70 years or more, and 60% of all deaths occurred among patients admitted to institutions outside hospitals. Within outbreaks in care homes in Norway, case fatality rates of 15 to 50% have been reported in 2020. Patients in care homes are not prioritized for any advanced supportive medical treatment for COVID-19, and mechanical ventilation is not an option in these institutions.

The WHO has provided strategic guidelines (WHO Roadmap) for prioritization of which treatment alternatives should be systematically tested, and included convalescence plasma an alternative to consider. Norwegian hospitals are already part of the WHO Solidarity treatment trial to evaluate the safety and efficacy of antiviral treatments. Based on the potential to provide an effective COVID-19 treatment with reliably local supply until a safe and effective vaccine is available, Norwegian blood banks led by the Norwegian Health Directorate have converged on a national project for the collection and testing of convalescence plasma.

At several leading centers in the world different variants of clinical trials are now underway to clarify the efficacy and safety of treatment with convalescence plasma. Several countries' health authorities (among others in the USA, Italy and Sweden) also allow use outside study settings, conditional to the reporting of data before and after transfusion to enable later efficacy evaluation (https://ccpp19.org/).

In Norway, plasma is being prepared in accordance with guidance from the European Blood Alliance (EBA) (https://ec.europa.eu/health/blood\_tissues\_organs/COVID-19). The Norwegian Directorate for Health has issued guidelines for the Norwegian blood banks to ensure adherence with the EBA guidance.

## 2.3. Benefit/Risk Assessment

Convalescent plasma has not yet been shown to be safe and effective as a treatment for COVID-19. A pre-publication study on safety in 5000 patients indicates that convalescent plasma treatment is safe, even to critically ill COVID-19 patients (Joyner et al 2020).

Potential Risk of Clinical	Summary of Data/Rationale	Mitigation Strategy
Significance	for Risk	Preparation of plasma
Risks commonly associated with transfusion	Low frequency, but higher risk for transfusion associated complications among elderly	according to EU guidelines for COVID- 19

